#### **9.4.2 Concomitant medication**

Concomitant medication will be coded using the WHO drug dictionary (Version March 2021 B3). Concomitant medication will be listed.

#### **9.4.3 Clinical laboratory parameters**

All clinical chemistry and hematology data will be summarized by parameter and treatment, and listed. Urinalysis data will be listed. Changes from baseline (Day -1) will also be presented. Additionally, clinical chemistry, hematology and urinalysis data outside the reference ranges will be listed and flagged on individual participant data listings.

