5.1. Inclusion Criteria

Participants are eligible to be included in the study only if all of the following criteria apply:

Age

1. Participant must be 18 to 65 years of age, inclusive, at the time of signing the informed consent.

Type of Participant and Disease Characteristics

2. Participants who are overtly healthy, as determined by medical evaluation including:
 - medical history
 - physical examination
 - clinical laboratory tests
 - ECG and
 - vital signs.
3. Have clinical laboratory test results within normal reference range for the population or investigative site, or results with acceptable deviations that are judged to be not clinically significant by the investigator
4. Have venous access sufficient to allow for blood sampling as per the protocol
5. Agree not to donate blood or plasma until after the end of their participation in the study
6. Are reliable and willing to make themselves available for the duration of the study and are willing to follow study procedures.

Weight

7. Body mass index within the range 18.0 to 32.0 kg/m² (inclusive).

Sex**8. Males and females.**

Contraceptive use by participants should be consistent with local regulations regarding the methods of contraception for those participating in clinical studies.

a. Male participants:

i. Males may participate in this study.

b. Female participants:

i. Women of childbearing potential may participate in this study.

ii. Women not of childbearing potential may participate in this study.

Please refer to Section 10.4 for definitions and additional guidance related to contraception.

Informed Consent**9. Capable of giving signed informed consent as described in Section 10.1, which includes compliance with the requirements and restrictions listed in the informed consent form (ICF) and in this protocol.****5.2. Exclusion Criteria**

Participants are excluded from the study if any of the following criteria apply:

Medical Conditions

1. Have known allergies to mirikizumab, related compounds, or any components of the formulation, or history of significant atopy
2. Have self-perceived dullness or loss of sensation in either arm or thigh or on either side of the abdomen
3. Have an abnormality in the 12-lead ECG that, in the opinion of the investigator, increases the risks associated with participating in the study
4. Have an abnormal blood pressure, pulse rate, or body temperature determined to be clinically significant by the investigator

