10.1. Appendix 1: Regulatory, Ethical, and Study Oversight Considerations

10.1.1. Regulatory and Ethical Considerations

This study will be conducted in accordance with the protocol and with the following:

- Consensus ethical principles derived from international guidelines including the Declaration of Helsinki and Council for International Organizations of Medical Sciences International Ethical Guidelines
- Applicable International Council for Harmonisation (ICH) good clinical practice (GCP) Guidelines
- Applicable laws and regulations.

The protocol, protocol amendments, ICF, IB, and other relevant documents (for example, advertisements) must be submitted to an IRB/IEC by the investigator and reviewed and approved by the IRB/IEC before the study is initiated.

Any amendments to the protocol will require IRB/IEC approval before implementation of changes made to the study design, except for changes necessary to eliminate an immediate hazard to study participants.

Protocols and any substantial amendments to the protocol will require health authority approval prior to initiation except for changes necessary to eliminate an immediate hazard to study participants.

The investigator will be responsible for the following:

- Providing written summaries of the status of the study to the IRB/IEC annually or more frequently in accordance with the requirements, policies, and procedures established by the IRB/IEC
- Notifying the IRB/IEC of SAEs or other significant safety findings as required by IRB/IEC procedures
- Providing oversight of study conduct for participants under their responsibility and adherence to requirements of 21 Code of Federal Regulations (CFR), ICH guidelines, the IRB/IEC, European regulation 536/2014 for clinical studies (if applicable), and all other applicable local regulations.

Investigator sites are compensated for participation in the study as detailed in the Clinical Trial Agreement.

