10.2. Appendix 2: Clinical Laboratory Tests

The tests detailed below will be performed by the central laboratory or local laboratory, as detailed in the table below.

In circumstances where the sponsor approves local laboratory testing in lieu of central laboratory testing (in the table below), the local laboratory must be qualified in accordance with applicable local regulations.

Protocol-specific requirements for inclusion or exclusion of participants are detailed in Section 5 of the protocol.

Additional tests may be performed at any time during the study as determined necessary by the investigator or required by local regulations.

Pregnancy testing will be conducted as detailed in the SoA (Section 1.3).

Investigators must document their review of the laboratory safety results.

Safety Laboratory Tests^a

Hematology	Clinical Chemistry
Hematocrit	Sodium
Hemoglobin	Potassium
Erythrocyte count (RBC)	Bicarbonate
Mean cell volume	Chloride
Mean cell hemoglobin	Calcium
Mean cell hemoglobin concentration	Phosphorous
Leukocytes (WBC)	Glucose
Cell morphology	BUN
Absolute counts and % of:	Uric acid
Neutrophils	Total cholesterol
Lymphocytes	Total protein
Monocytes	Albumin
Eosinophils	Total bilirubin
Basophils	Direct bilirubin
Platelets	ALP
Urinalysis	AST
Specific gravity	ALT
pH	Creatinine
Protein	
Glucose	Other Tests
Ketones	Ethanol testing ^{c,d}
Bilirubin	Urine drug screen ^d
Urobilinogen	Pregnancy test (females only) ^e
Blood	FSH (females only) ^b
Nitrite	QuantiFERON®-TB Gold ^b
Microscopy (if dipstick abnormal; blood, protein, or nitrites)	
Serology	
Hepatitis B surface antigen ^b	
Hepatitis B core antibody ^b	
Hepatitis C antibody ^b	
HIV ^b	

Abbreviations: ALP = alkaline phosphatase; ALT = alanine aminotransferase; AST = aspartate aminotransferase;

BUN = blood urea nitrogen; FSH = follicle-stimulating hormone; HIV = human immunodeficiency virus;

RBC = red blood cell; TB = tuberculosis; WBC = white blood cell.

^a Performed locally at screening and Day -1 and centrally at all postdose time points unless otherwise stated.

^b Performed at screening only.

^c Urine ethanol test will be conducted at screening and a breath-test will be performed at check-in on Day -1.

^d Urine drug screen and ethanol tests may be repeated locally at additional time points at the discretion of the investigator.

^e Serum pregnancy test to be performed at screening and Day -1. Urine pregnancy test to be performed locally at Day 85 or early discontinuation.

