10.2.1. Blood Sampling Summary

This table summarizes the approximate number of venipunctures and blood volumes for all blood sampling (screening, safety laboratories, and bioanalytical assays) during the study.

Protocol I6T-MC-AMBX Sampling Summary

Purpose	Maximum Blood Volume per Sample (mL)	Number of Blood Samples	Total Volume (mL)
Screening tests ^a	45	1	45
Local clinical laboratory and pregnancy tests ^a	12.5	1	12.5
Central clinical laboratory tests ^a	4.5	4	18
Pharmacokinetics	3	15 ^b	45
Immunogenicity	10	4	40
Pharmacogenetics	10	1	10
Total			170.5
Total for clinical purposes			175

^a Additional samples may be drawn if needed for safety purposes.

^b Includes additional 3 samples, if required.

10.3. Appendix 3: Adverse Events: Definitions and Procedures for Recording, Evaluating, Follow-up, and Reporting

The definitions and procedures detailed in this appendix are in accordance with International Organization for Standardization 14155.

Both the investigator and the sponsor will comply with all local medical device reporting requirements.

The detection and documentation procedures described in this protocol apply to all sponsor medical devices provided for use in the study. See Section [6.1.2](#) for the list of sponsor medical devices.

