### 3. INTRODUCTION

This SAP has been developed after review of the Clinical Study Protocol (final version dated 11 August 2021).

This SAP describes the planned analysis of the safety, tolerability and pharmacokinetic (PK) data from this study. A detailed description of the planned TFLs to be presented in the clinical study report (CSR) is provided in the accompanying TFL shell document.

The intent of this document is to provide guidance for the statistical and PK analyses of data. In general, the analyses are based on information from the protocol, unless they have been modified by agreement with Eli Lilly and Company. A limited amount of information concerning this study (e.g., objectives, study design) is given to help the reader's interpretation. For open-label studies, this SAP must be signed off prior to first participant visit for this study. When the SAP and TFL shells are agreed upon and finalized, they will serve as the template for this study's CSR.

This SAP supersedes the statistical considerations identified in the protocol; where considerations are substantially different, they will be so identified. If additional analyses are required to supplement the planned analyses described in this SAP, they may be performed and will be identified in the CSR. Any substantial deviations from this SAP will be agreed upon with Eli Lilly and Company and identified in the CSR. Any minor deviations from the TFLs may not be documented in the CSR.

This SAP is written with consideration of the recommendations outlined in the International Conference on Harmonisation (ICH) E9 Guideline entitled Guidance for Industry: Statistical Principles for Clinical Trials and the ICH E3 Guideline entitled Guidance for Industry: Structure and Content of Clinical Study Reports.

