## 9. STATISTICAL METHODOLOGY

### 9.1 General

Data listings will be provided for all data that is databased. Summary statistics and statistical analysis will only be presented for data where detailed in this SAP. For continuous data, summary statistics will include the arithmetic mean, arithmetic standard deviation (SD), median, minimum, maximum and n; for log-normal data (e.g. the PK parameters: AUCs and  $C_{max}$ ) the geometric mean and geometric (CV%) will also be presented. For categorical data, frequency count and percentages will be presented. Data listings will be provided for all participants up to the point of withdrawal, with any participants excluded from the relevant population highlighted. Summary statistics and statistical analyses will generally only be performed for participants included in the relevant analysis population. For the calculation of summary statistics and statistical analysis, unrounded data will be used.

Mean change from baseline is the mean of all individual participants' change from baseline values. Each individual change from baseline will be calculated by subtracting the individual participant's baseline value from the value at the timepoint. The individual participant's change from baseline values will be used to calculate the mean change from baseline using a SAS procedure such as Proc Univariate.

Data analysis will be performed using SAS® Version 9.4 or greater.

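### Laboratory change from baseline is by default a central value minus a local one, so the descriptive within-arm change tables may carry a between-laboratory offset

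*SAP*

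**What the plan says.** SAP 9.4.3 tabulates chemistry and hematology by parameter and treatment and states: "Changes from baseline (Day -1) will also be presented". SAP 9.1 gives the arithmetic: "Each individual change from baseline will be calculated by subtracting the individual" participant's baseline from the later value.

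Protocol Appendix 2 (Section 10.2), footnote a, says where safety samples are tested: "Performed locally at screening and Day -1 and centrally at all postdose time points unless otherwise stated". This is a default, because the appendix also allows exceptions ("In circumstances where the sponsor approves local laboratory testing in lieu of central laboratory testing"). The blood sampling summary in Section 10.2.1 has one screening draw, one local draw and four draws under "Central clinical laboratory tests".

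Protocol 9.3.3.2 calls the baseline predose and names no laboratory. SAP 9.4.3 marks results outside reference ranges, but only in listings. SAP 9.4.13 rules out inferential safety analyses. Neither document says how the summaries handle the change of laboratory. The SAP introduction says that the detailed description of the tables "is provided in the accompanying TFL shell document"; neither that document nor the laboratory manual was available.

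**The concern.** When baseline and follow-up come from different laboratories, a difference in method or calibration enters every individual change. Both arms receive 300 mg mirikizumab, so there is no untreated group in which such an offset would show itself. A reader would naturally take the within-arm change as the effect of the drug. Hematology is where this matters most, since Protocol 2.2.1 reports symptom-free falls in neutrophil count in some participants.

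The study is multi-site, and inclusion criterion 3 accepts site reference ranges ("Have clinical laboratory test results within normal reference range for the population or investigative site"). More than one local laboratory may therefore be involved, and any offset could differ by site. The documents do not show that it does.

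**Working it through.** **1. Which laboratory supplies which value.** SAP 9.4.3 fixes the baseline at Day -1. Footnote a makes Day -1 local and post-dose central. SAP 9.1 subtracts one from the other. The default change is therefore central minus local.

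**2. Does the sampling plan agree?** Section 10.2.1 has 1 screening + 1 local + 4 central = 6 draws. The laboratory row of the Schedule of Activities (Protocol 1.3) has 6 marks. Taking away screening and Day -1 leaves 4, equal to the 4 central draws. The volumes add up as printed: 45 + 12.5 + 18 + 45 + 40 + 10 = 170.5 mL.

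**3. Which four days?** Protocol 5.3.3 names five laboratory visits after Day -1 (Days 1, 3, 15, 29 and 85), one more than the draws allow. Column alignment in the schedule was lost in text extraction, so the spacing of the marks has to serve. The first of the four marks is followed by one four columns later and another two columns after that.

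- Starting at Day 3, those steps land on Days 15 and 29, both named in 5.3.3.
- Starting at Day 1, they land on Days 11 and 22, neither of which is named.

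Days 3, 15, 29 and 85 are the most consistent reading, but not a certain one. If a Day 1 predose sample does exist, SAP 9.4.3 still takes Day -1 as baseline.

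**4. What an offset does.** Let a laboratory add a constant to the true value: *c* for central, *l* for local.

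- Post-dose minus Day -1 = true change + (*c* − *l*). The mean over an arm is the mean true change plus the participant-weighted mean offset, whatever the sample size.
- AI minus PFS: the same expected offset sits in both arms and cancels in expectation.
- Central Day *t* minus central Day 85 = true difference + (*c* − *c*). The offset drops out.

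**5. Scale (illustration only).** Neither the offset nor the SD of individual change is in the documents, and no intervals are planned. The offset that equals the 95% half-width of a mean change is 1.96/√n, in units of that SD:

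| Group | n | Offset (SD) |
|---|---|---|
| Both arms pooled | 216 | 1.96/√216 = 0.13 |
| One device arm | 108 | 1.96/√108 = 0.19 |
| One device-by-site group | 216/6 = 36 | 1.96/√36 = 0.33 |

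The last row applies if treatment in SAP 9.4.3 means the six groups listed in SAP 6. At n = 108 the standard error is 1/√108 = 0.096 SD, so assumed offsets of 0, 0.1, 0.2 and 0.5 SD equal 0, 1.0, 2.1 and 5.2 standard errors with no drug effect at all.

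**6. Is Day 85 a usable comparator?** Day 85 ±3 days is 81 to 87 days after dosing. At the half-life of about 10 days in Protocol 2.2.4 this is 8.1 to 8.7 half-lives. Ignoring absorption time, 2^−8.1 = 0.36% to 2^−8.7 = 0.24% remains. This holds for completers, not for early-discontinuation visits.

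**The case against.** The strongest reply concerns consequence. Central values at the early visits and at Day 85 are already planned output. A constant laboratory offset would appear at all of them, while an effect that follows concentration would fade by Day 85. A reader might infer that an offset could not be told apart from a drug effect; the plan's own data do not support so strong a statement, at least for completers. This part of the reply stands. It assumes that the central method is stable over time and that any effect wears off with the drug.

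Second, Protocol 5.3.3 names Day 1. A reader might infer from Section 10.2.1 that there is certainly no central predose sample. The mark spacing makes a Day 1 predose draw unlikely but does not exclude it, and footnote a does not assign a laboratory to one.

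Third, individual safety signals are covered elsewhere: out-of-range flags and listings (SAP 9.4.3), investigator review and AE reporting (Protocol 8.2.4), and hepatic repeat testing (Protocol 8.2.6.1). This also stands and limits the point to the summary tables.

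Fourth, the offset may be zero, the SD yardstick rests on an SD that is not given, and site differences are possible rather than shown. All true. None of this changes the fact that the planned subtraction crosses laboratories without saying so.

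**Conclusion.** The point holds as a minor one. By default, the chemistry and hematology change tables subtract a local Day -1 value from central post-dose values and may contain a between-laboratory offset of unknown, possibly zero, size. The visible documents establish possible mixing, not a bias.

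Primary PK, the TEAE/SAE endpoints and the out-of-range flags do not use this subtraction. The AI-PFS contrast is unaffected in expectation, so a reader should not infer that the device comparison of safety is compromised.

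The conclusion rests on footnote a applying as written, without sponsor-approved local testing after dosing, and on the unseen table shells and laboratory manual not already dealing with the matter. Separately, Protocol 5.3.3 should be reconciled with the Schedule of Activities and Section 10.2.1 on whether Day 1 is a laboratory visit.

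**What to change.** **Recommended, SAP and table shells only.** Keep the raw change from Day -1 and add:

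- shift tables in which each value is classified against the reference range of the laboratory that reported it;
- a central-only, within-participant comparison of Days 3, 15 and 29 with Day 85, for completers;
- a footnote that baseline and post-dose values come from different laboratories.

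This uses data already planned. It costs a little programming. Shift tables are coarser than raw change and are only as comparable as the reference ranges behind them. Non-completers have no Day 85 comparator: at most about 240 − 216 = 24 participants, fewer if some of these were randomized but never dosed and so have no post-dose change at all.

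**Optional, if the protocol is being amended anyway.** Send one central tube of about 4.5 mL from the existing Day -1 draw, use it as the baseline for change, and keep the local result for eligibility. Central draws go from 4 to 5 and central volume from 18 to 5 × 4.5 = 22.5 mL, with no extra visit or venipuncture, but up to about 240 extra panels. Footnote a and Section 10.2.1 would need to change, and Section 10.1.1 applies: "Any amendments to the protocol will require IRB/IEC approval before implementation of changes made to the study design". For descriptive tables alone, whether that is worth the cost is open to debate.

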4.1. Overall Design

Study AMBX is a Phase 1, open-label, 2-arm, randomized, parallel-design, single-dose, multi-site study in healthy participants.

Screening

All participants will be screened within 28 days prior to enrollment. At screening, participants will be stratified into 1 of 3 weight categories (less than 70 kg, 70 to 80 kg, and more than 80 kg).

Treatment and Assessment Period

Eligible participants will be admitted to the clinical research unit (CRU) on Day -1.

Within the 3 weight categories, participants will be randomized ([Table AMBX.1](#)) using a computer-generated allocation code (Section [6.3](#)):

- 1:1 to delivery device (either PFS [reference] or AI [test])
- within each delivery-device group 1:1:1 to injection-site (arm, thigh, or abdomen)

On Day 1, participants will receive a total of 3 mL (300 mg mirikizumab) as 2 SC injections of 1 mL and 2 mL delivered via PFS or AI in the location assigned by the randomization.

Participants may be allowed to leave the CRU after completing the 4-hour safety assessments on Day 1, or later at the investigator's discretion, and will return for PK and immunogenicity sampling and safety assessments at predefined times up to 12 weeks postdose. Participants will be monitored for safety between outpatient visits by way of telephone assessment.

Safety and tolerability will be assessed through clinical laboratory tests, vital signs measurements, ECGs, recording of adverse events, recording of injection-site reactions, and physical examination.

Table AMBX.1. Study AMBX Stratification and Randomization Plan

Weight Category (Participants) ^a	Injection Device	Subcutaneous Injection Location ^b	Desired Number of Participants
Low <70 kg (~72 participants)	1 x 1-mL + 1 x 2-mL PFS (Reference) or 1 x 1-mL + 1 x 2-mL AI (Test)	Arm	12
	1 x 1-mL + 1 x 2-mL PFS (Reference) or 1 x 1-mL + 1 x 2-mL AI (Test)	Abdomen	12
	1 x 1-mL + 1 x 2-mL PFS (Reference) or 1 x 1-mL + 1 x 2-mL AI (Test)	Thigh	12
Medium 70 – 80 kg (~72 participants)	1 x 1-mL + 1 x 2-mL PFS (Reference) or 1 x 1-mL + 1 x 2-mL AI (Test)	Arm	12
	1 x 1-mL + 1 x 2-mL PFS (Reference) or 1 x 1-mL + 1 x 2-mL AI (Test)	Abdomen	12
	1 x 1-mL + 1 x 2-mL PFS (Reference) or 1 x 1-mL + 1 x 2-mL AI (Test)	Thigh	12
High >80 kg (~72 participants)	1 x 1-mL + 1 x 2-mL PFS (Reference) or 1 x 1-mL + 1 x 2-mL AI (Test)	Arm	12
	1 x 1-mL + 1 x 2-mL PFS (Reference) or 1 x 1-mL + 1 x 2-mL AI (Test)	Abdomen	12

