5.3.3. Activity

Participants will be advised to maintain their regular levels of physical activity/exercise; however, they should not undertake vigorous or prolonged exercise within 48 hours prior to any visit in which laboratory safety tests will occur (Screening, Day -1, Day 1, Day 3, Day 15, Day 29, and Day 85). While certain study procedures are in progress at the site, participants may be required to remain recumbent or sitting.

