9.3.3.2. Statistical Evaluation of Safety

Safety parameters that will be assessed include clinical laboratory parameters and vital signs. The parameters and changes from baseline (predose), where appropriate, will be listed and summarized using standard descriptive statistics. Additional analyses will be performed if warranted upon review of the data.

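### Laboratory change from baseline subtracts a local Day -1 value from central postdose values, so within-arm changes, including neutrophils, carry a between-laboratory difference of unknown size

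*SAP*

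**What the plan says.** SAP 9.4.3 plans summaries of all chemistry and hematology data by parameter and treatment, and adds: "Changes from baseline (Day -1) will also be presented". SAP 9.1 defines an individual change as the value at the timepoint minus that participant's baseline, with no term for the laboratory. Protocol 9.3.3.2 is looser. It calls the baseline predose and names no laboratory: "The parameters and changes from baseline (predose), where appropriate, will be listed and summarized using standard descriptive statistics".

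Footnote a to the safety laboratory table in Protocol Appendix 2 (Section 10.2) says where the samples are tested: "Performed locally at screening and Day -1 and centrally at all postdose time points unless otherwise stated". Where the sponsor approves local testing in place of central testing, "the local laboratory must be qualified in accordance with applicable local regulations". The sampling summary in Section 10.2.1 counts one local clinical laboratory sample apart from screening, and four samples under "Central clinical laboratory tests". Section 4.1 describes a "single-dose, multi-site study in healthy participants", so there may be several local laboratories.

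Protocol 2.2.1 reports asymptomatic falls in neutrophil counts in a minority of earlier participants. Absolute neutrophils are in the Appendix 2 panel.

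**The concern.** A change from baseline is meant to remove what is constant within a person and leave what happened after dosing. Here the measuring laboratory changes between the baseline and the scheduled postdose values, so the subtraction leaves a laboratory difference behind. Every participant receives 300 mg of mirikizumab, and there is no placebo or untreated arm in which that difference would show by itself.

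Neither document describes a paired sample, a bridging step, an adjustment, or a comparison of each value with its own laboratory's range. Requiring local laboratories to be qualified does not make their results interchangeable with central ones.

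What is at stake is the reading of a descriptive safety table. A reader looking for the neutrophil falls named in the protocol would turn to the change table. A central laboratory that reads low could make a fall appear there, and one that reads high could mask a fall.

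**Working it through.** **1. Which samples are local and which are central.** The sampling summary reproduces: 4 x 4.5 mL = 18 mL central, and 45 + 12.5 + 18 + 45 + 40 + 10 = 170.5 mL in total. Protocol 5.3.3 lists laboratory visits at screening and Days -1, 1, 3, 15, 29 and 85. With footnote a, the four central samples fit Days 3, 15, 29 and 85. This is an inference. The laboratory row of the schedule is broken in the text available, and a Day 1 predose central sample cannot be confirmed. If one exists, SAP 9.4.3 still does not use it as baseline.

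**2. What the subtraction contains.** Let T be the true value, and let l and c be the offsets of the local and central laboratories.

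- Planned change: (T_post + c) - (T_Day-1 + l) = true change + (c - l).
- Autoinjector minus pre-filled syringe: (c - l) has the same expectation in both randomized arms, so it cancels in expectation.
- Central visits only: (T_d + c) - (T_85 + c) = T_d - T_85, so the offset drops out. If the offset is proportional, it only rescales the difference. For example, a true difference of 1.0 would read as 0.95 at a 5% low reading.

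**3. How large it could be.** No input here is in the documents. The assumptions are a mean neutrophil count of 4.0 x10^9/L (range 3.0 to 5.0), an SD of individual change of 1.0, no drug effect, and one common offset across sites. Shift in mean change = offset x mean:

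| Central reads lower by | Mean 4.0 | Means 3.0 to 5.0 |
|---|---|---|
| 0% | 0 | 0 |
| 2% | -0.08 | -0.06 to -0.10 |
| 5% | -0.20 | -0.15 to -0.25 |
| 10% | -0.40 | -0.30 to -0.50 |

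The signs reverse if the central laboratory reads higher. As a yardstick only, the standard error of a mean change with 108 per arm is 1.0/sqrt(108) = 0.096. At mean 4.0 the shifts are then 0.83, 2.08 and 4.16 standard errors. A common offset does not shrink as participants are added.

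**4. Against the signal.** A true fall of 1.0 in 5% or 10% of participants moves the mean by 0.05 x 1.0 = 0.05 or 0.10 x 1.0 = 0.10. Under these assumptions a 2% laboratory difference (0.08) is already of that order.

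**5. Is Day 85 a usable reference?** Day 85 is 84 days postdose, and Protocol 2.2.4 gives a half-life of about 10 days. So 84/10 = 8.4 half-lives have passed, and 0.5^8.4 = 0.003, or about 0.3%, of drug remains.

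**The case against.** The strongest reply is that the planned output already holds a same-laboratory comparison. SAP 9.4.3 summarizes the values as well as the changes, and the central visits are comparable with one another. A laboratory offset would persist to Day 85, whereas a fall that follows exposure would appear early and recover. This stands. A reader might infer that the plan leaves a neutrophil fall indistinguishable from a laboratory difference. The documents do not support that: the confounding lies in the Day -1 change table, not in the data as a whole.

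It is also fair that mean change is a weak tool for a signal confined to a minority, even with a central baseline. Out-of-range flags, reporting of clinically relevant laboratory changes as adverse events (Protocol 8.2.4) and the sponsor's periodic review of analytes (Protocol 8.2.6) catch such cases better, and none of them uses the subtraction. They do not show falls that stay within range.

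A reader might also take the illustrated shifts as evidence of a material bias. They are not. The true offset may be small, and offsets of opposite sign at different sites would partly cancel in the mean. No inferential safety analysis is planned.

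Nor is every postdose value necessarily central, since footnote a allows exceptions and the sponsor may approve local testing. Finally, the table shells named in SAP section 3 and the laboratory manual were not available for review. Either might already carry a caveat.

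**Conclusion.** The point holds as a limited defect in a descriptive table. As scheduled, within-arm changes from Day -1 in chemistry and hematology mix any drug effect with a local-to-central difference, and neither document says so. The documents establish the mixing but not its size. The illustrative shifts of 0 to 0.40 x10^9/L at a mean of 4.0 rest wholly on assumed values.

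It would be wrong to infer that the device comparison or the bioequivalence conclusion is at risk. Randomization balances the offset between devices in expectation, and the pharmacokinetic analysis does not use these laboratory results. Range flags and adverse event reporting also stand. A cheap change to the analysis is warranted. The finding does not by itself justify a protocol amendment.

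**What to change.** Make three additions to SAP 9.4.3, using samples already planned:

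1. Label the Day -1 change tables as local-to-central, in the text and in a table footnote.
2. Add a low / in-range / high shift table from Day -1 to each postdose visit, with each value judged against the range of the laboratory that measured it. For neutrophils, include a row for not low at Day -1 to low postdose.
3. Present within-central changes: Days 3, 15 and 29 relative to Day 85. Use the laboratory recorded for each result, so that any locally tested postdose value is left out. Do not let an early discontinuation sample stand in for Day 85.

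The cost is a few sentences, a footnote and two sets of tables. SAP 9.4.3 already plans range flags, so the reference ranges should be held; each must be linked to its laboratory. There are two downsides. The shift table misses falls that stay in range, and the Day 85 comparison assumes recovery by then and loses participants without a Day 85 sample.

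A paired central tube at the Day -1 draw would give a like-for-like baseline and measure the offset directly. It is optional, and worth adding only if the protocol is being amended anyway. It would cost up to about 240 extra central panels and 4.5 mL per participant. The planned total would rise from 170.5 to 175.0 mL, which uses up the whole of the 175 mL shown as "Total for clinical purposes" in Section 10.2.1.
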